6.2.1.2.3 Dose-limiting Toxicity Definition

An adverse event will be considered related to study treatment (possibly, probably, or definitely related to the study treatment) if there is a suspected “reasonable causal relationship” to the study treatment (ICH E2A), and not only a lack of an alternative explanation for the toxicity. All toxicities will be graded using the CTCAE version 4.0 ([Appendix A](#)).

The occurrence of any of the following toxicities during DLT evaluation period (ie, 21 day period from the initial administration of AMG 820 and pembrolizumab in combination) will be considered a DLT, if judged by the investigator to be related to the administration of AMG 820 and/or pembrolizumab:

- Grade 4 non-hematologic toxicity
- Grade 3 or higher pneumonitis
- Grade 3 non-hematologic toxicity lasting > 7 days despite appropriate treatment
 - Grade 3 fatigue will not be classified as DLT, irrespective of duration
- Any grade 3 or higher non-hematologic laboratory value if:
 - medical intervention is required, or
 - the abnormality leads to hospitalization, or
 - the abnormality persists at grade 3 or higher for >1 week unless deemed not clinically important per both investigator and sponsor
- Grade 3 or grade 4 febrile neutropenia

- Grade 3 or higher thrombocytopenia with bleeding and Grade 4 or higher thrombocytopenia lasting > 48 hours or any thrombocytopenia requiring intervention
- Delay in cycle 2 treatment for > 2 weeks due to study drug-related toxicity (unless clearly attributable to pembrolizumab only and delay is caused due to tapering of steroids)
- Any other intolerable toxicity leading to permanent discontinuation of AMG 820 or pembrolizumab

Lymphopenia of any grade is not considered a DLT

Dose limiting toxicities do not include the following:

- A transient (resolving to grade ≤ 1 within 6 hours of onset) grade 3 infusion-related adverse event
- Any grade 3 endocrinopathy that is adequately controlled by hormonal replacement

Cumulative adverse events profile will be taken into consideration when making decisions on dose escalation or de-escalation.

If an AE is clearly attributable to pembrolizumab (based on its known safety profile) and does not exceed the expected severity, this specific AE may be considered exempt from being a DLT.

Disease related events should not be considered a DLT.

Any subject meeting the criteria for Hy's Law case (ie, severe drug-induced liver injury) will be considered a DLT. A Hy's Law case is defined as: AST or ALT values of $\geq 3 \times$ ULN AND with serum total bilirubin level (TBL) of $> 2 \times$ ULN without signs of cholestasis and with no other clear alternative reason to explain the observed liver-related laboratory abnormalities (see [Section 6.4](#) on hepatotoxicity management and [Appendix A](#) for further explanation of Hy's law case and Management of Hepatic Function).

If a subject experiences a DLT during the DLT evaluation period, study treatment should be discontinued for that subject. Additionally, any treatment related toxicity meeting the DLT definition after day 21 should result in discontinuation of therapy. In subjects with irPR, irCR or evidence of clinical benefit (as determined by the investigator), an option to continue at the same or at a reduced dose level can be considered once the toxicity returns to the subject's baseline value or CTCAE grade ≤ 1 if deemed appropriate by the investigator and sponsor.

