3.4 Replacement of Subjects

Subjects enrolled may be replaced if they are not evaluable for DLT (eg, a subject did not receive study treatment, or ended the study treatment before completion of DLT evaluation period for a reason other than experiencing a DLT).

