### Dose Limiting Toxicity

A DLT will be defined as any grade  $\geq 3$  adverse event occurring during a DLT window (21 day period from the initial administration of AMG 820 and pembrolizumab in

combination), and if judged by the investigator to be related to the administration of AMG 820 and/or pembrolizumab.

For details see the Section 6.2.1.2.3 of the protocol.

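### The DLT definition behind the 6+3 rule is inconsistent within the protocol and between protocol and SAP, so the same events can give different DLT counts

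*Protocol*

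**What the plan says.** Protocol Section 6.2.1.2.3 lists the toxicities that count as a DLT if they are related and fall in the first 21 days. Upper grades are written in two ways:

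- Closed at grade 4: "Grade 4 non-hematologic toxicity" and "Grade 3 or grade 4 febrile neutropenia".
- Open upward: "Grade 3 or higher pneumonitis", "Any grade 3 or higher non-hematologic laboratory value if" one of three conditions is met, and the thrombocytopenia bullet.

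The thrombocytopenia bullet reads "Grade 3 or higher thrombocytopenia with bleeding and Grade 4 or higher thrombocytopenia lasting > 48 hours or any thrombocytopenia requiring intervention". The list also has a catch-all, "Any other intolerable toxicity leading to permanent discontinuation of AMG 820 or pembrolizumab", and the section makes any Hy's Law case a DLT.

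SAP Section 6 gives its own short definition. It begins "A DLT will be defined as any grade" and sets the floor at grade 3, for related events in the 21-day window. It then sends the reader to protocol Section 6.2.1.2.3 for details.

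On evaluability, protocol Section 3.1.1 (repeated in SAP Section 3.1.1) removes a subject who drops out in cycle 1 only if the reason was not a related adverse event. Protocol Sections 3.4 and 6.2.1.2.2 allow replacement of a subject who "ended the study treatment before completion of DLT evaluation period for a reason other than experiencing a DLT". SAP Section 7.2 takes its DLT analysis set from Section 6.2.1.2.2.

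**The concern.** The DLT count is a primary endpoint and the stated input to the cohort rule: 0 or 1 of 6 is tolerable, 2 of 6 adds three subjects, 3 or more is not tolerable. With 6 to 9 subjects, a single classification can matter, so the definition has to give one answer per event. It does not always do so.

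Because one list mixes open and closed upper grades, a closed limit can be read as deliberate. Assuming the usual CTCAE convention that a fatal event is grade 5 (the documents cite the scale without reproducing it), a related death can fall above the ceiling of the bullet that would otherwise apply. The evaluability texts then disagree on whether a subject who stopped for a related event not classed as a DLT stays in the denominator. The SAP's summary would count events that the protocol list leaves out, so the reported count could also differ from the one used for dosing.

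**Working it through.** **The plan's own figure.** Protocol Section 10.2 gives a 47-91% chance of at least one DLT in 6 at true rates of 10-33%. 1 − 0.90^6 = 46.9% and 1 − 0.67^6 = 91.0%. It reproduces and is not in dispute.

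**The texts side by side.**

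1. *Fatal events.* Fatal pneumonitis is covered by its own bullet. Hy's Law cases are covered separately. A laboratory abnormality of grade 3 or above that meets one of its conditions is covered. What remains is a related death outside these groups with no qualifying grade recorded beforehand. Only the catch-all can reach it.
2. *Thrombocytopenia.* If both conditions joined by *and* are required, the first threshold (grade 3 or above) does no work, because the second (grade 4 or above) already implies it. Read literally, two cases are not DLTs unless intervention is required: grade 3 with bleeding, and grade 4 lasting more than 48 hours without bleeding.
3. *SAP against protocol.* A related grade 3 fatigue in the window is a DLT under the SAP sentence and expressly not one under the protocol. The same holds for a related grade 3 non-hematologic toxicity that resolves within 7 days and meets no other bullet.
4. *Evaluability.* A subject who stops in cycle 1 for a related event not classed as a DLT is not removed by Section 3.1.1 but may be replaced under Sections 3.4 and 6.2.1.2.2.

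**When an uncounted event matters.** Going from 1 to 0 of 6 changes nothing. Going from 2 to 1 of 6 turns *add three* into *tolerable*. Going from 3 to 2 of 6 turns *not tolerable* into *add three*.

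**Illustrative size.** Let X_n be binomial(n, p), with p the DLT probability in the other subjects. The documents give no value for p; 20%, 25% and 33% are assumed. I use the reading in Section 3.1.1, where 3 or more DLTs is not tolerable. Section 6.2.1.2.2 states that limit as 33% or more, which 2 of 6 (33.3%) also meets. One of the first 6 subjects has a related event.

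- Counted: P(X5=0) + P(X5=1)·P(X3=0)
- Not counted, subject replaced: P(X6≤1) + P(X6=2)·P(X3=0)
- Not counted, subject kept: P(X5≤1) + P(X5=2)·P(X3=0)

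At p = 20%: 0.328 + 0.410 × 0.512 = 0.537; 0.262 + 0.393 + 0.246 × 0.512 = 0.781; 0.328 + 0.410 + 0.205 × 0.512 = 0.842.

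| p in the others | Counted | Not counted, replaced | Not counted, kept |
|---|---|---|---|
| 20% | 53.7% | 78.1% | 84.2% |
| 25% | 40.4% | 65.9% | 74.4% |
| 33% | 23.5% | 45.7% | 56.6% |

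Counted against replaced, the gap is 22 to 25 percentage points.

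**A second view.** Suppose a share m of qualifying events goes uncounted (assumed, 10-30%). The effective rate is p(1−m) if subjects are kept, or p(1−m)/(1−pm) if they are replaced. At p = 33%, the chance of declaring the dose tolerable is 46% with nothing missed. With m = 10%, 20% and 30% it is 51%, 58% and 64% if replaced, and 54%, 62% and 71% if kept.

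**The case against.** A reader might infer that the list leaves out treatment-related deaths as a class, so that a fatal toxicity could pass unnoticed into Part 2. The documents do not support that. Besides the bullets already named, protocol Section 9.2.2.1 asks for a separate record at each severity level, and the SAP repeats this. A colitis recorded at grade 4, or a febrile neutropenia recorded at grade 3 or 4, has met its bullet before any death. A fatal toxicity also ends treatment for good, so the catch-all can reasonably be read to include it.

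A reader might also infer that such a death leaves both numerator and denominator. Section 3.1.1 points the other way, since it keeps a subject lost to a related event. Nor does every misclassified event move the decision, as 0 and 1 of 6 are treated alike.

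There is a human safeguard too. Under Section 10.3.2 the DLRT reviews all grade 3 or higher toxicities that are not DLTs, and its decisions must be unanimous. Section 6.2.1.2.3 also brings in the cumulative adverse event profile. For thrombocytopenia, the intervention clause captures treated cases, and the Amendment 1 summary has a comma before *and*, which suggests separate criteria.

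Most of this stands and narrows the gap for fatal events to a residue. It does not remove the inconsistency. Events outside the DLT criteria only *may* enter the DLRT's decision, and there is no charter. The literal thrombocytopenia wording, the SAP-protocol difference and the two evaluability rules remain as written. The Amendment 2 rationale says the sponsor has stopped investigating the combination, so the effect on future dosing is limited. The SAP covers the final analysis, however, and its DLT summary still needs one definition.

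**Conclusion.** The point holds as an inconsistency in a stated decision rule, not as a wholesale omission of deaths. Three conflicts need settling: mixed upper grades and an ambiguous *and* in protocol Section 6.2.1.2.3; a SAP definition that gives a different count from the list it defers to; and two evaluability rules that part ways after a related event not classed as a DLT.

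An uncounted event matters only at 1 versus 2 or 2 versus 3 DLTs. The 22 to 25 point shift applies given one such event among the first 6, rates of 20-33% in the others, and replacement of the subject. It is not an estimate of how often this would happen, and the documents give no basis for one. Confidence is high on the textual conflicts and moderate on their practical weight, given the DLRT review.

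**What to change.** - Reconcile protocol Section 6.2.1.2.3 with SAP Section 6 so that one DLT definition applies, with the upper grade stated the same way in every bullet and the classification of a related fatal event made explicit.
- List the thrombocytopenia conditions separately, so that it is clear which are joint and which are alternatives.
- Reconcile protocol Sections 3.1.1, 3.4 and 6.2.1.2.2 and SAP Section 3.1.1 on evaluability and replacement after a related event, fatal ones included.
- For the final analysis, name the definition behind the DLT summary and list any event in the window that the two current definitions would classify differently.

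The clinical thresholds and rules themselves are for the sponsor to settle. The cost is wording in a few sections and one short listing from data already collected.

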3.1.1 Phase 1b Study Design (Part 1)

Part 1 of the study has a single-arm 6+3 design aimed at assessing the safety of the selected starting dose of AMG 820 in combination with pembrolizumab. It will be conducted in subjects with select advanced solid tumors (CRC, pancreatic cancer, NSCLC and potentially other tumor types as per eligibility criteria). If the selected starting dose is determined not tolerable following review of safety data, additional lower dose levels will be evaluated. Up to 3 cohorts will be evaluated for safety and will include at least 6 subjects per cohort, and up to 18 subjects in total. The initial cohort will treat subjects at the selected starting dose of 1400 mg AMG 820 plus 200 mg pembrolizumab Q3W. The period for evaluation of a DLT in cycle 1 is 21 days. A

subject is not DLT-evaluable if he/she drops out before completion of cycle 1 for reasons other than an adverse event related to study drug.

- If 0 or 1 of the initial 6 evaluable subjects experience a dose-limiting toxicity (DLT) then the dose combination will be determined to be tolerable and Part 2 initiated.
- If 2 of the initial 6 evaluable subjects experience a DLT then 3 additional evaluable subjects will be enrolled.
- If 3 or more of the evaluable subjects experience a DLT (eg, 33% or higher with 9 evaluable subjects) then the dose combination will be determined to be non-tolerable and a second Part 1 cohort will be enrolled to test a decreased dose of AMG 820 in combination with 200 mg pembrolizumab. Further degree of dose modification and/or schedule of administration will be decided based on analysis of emerging safety and PK data.

Prior to opening a subsequent cohort for enrollment, the Dose Level Review Team (DLRT) will evaluate data from subjects enrolled into prior cohorts (at least 21 days of safety follow-up) including events with a longer onset time or events following exposure to multiple doses. If late onset events occur during a cohort, the DLRT may adaptively re-consider the doses evaluated within a cohort for subsequent dosing and/or possibly trigger a de-escalation or withholding of additional doses in subsequent cohorts.

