6.2.1.2.2 Rules for DLT Evaluation in Part 1 of the study

The DLT evaluation period for a subject is 21 days from the initial administration of study treatment. To be evaluable for a DLT, subjects must have had the opportunity to be on treatment for at least 21 days from the initial dosing of study treatment and have received at least 1 dose of AMG 820 and 1 dose of pembrolizumab in combination, or have a DLT during the DLT evaluation period after at least 1 dose of AMG 820 and pembrolizumab. Subjects may be replaced if they are not evaluable for DLT to obtain at least 6 DLT-evaluable subjects in a cohort during Study Part 1 (eg, a subject did not receive study treatment, or ended the study treatment before completion of DLT evaluation period for a reason other than experiencing a DLT).

Safety will be evaluated considering the incidence of DLTs among all DLT-evaluable subjects enrolled in part 1, which will include up to 3 cohorts. The initial cohort will treat subjects with 1400 mg AMG 820 plus 200 mg pembrolizumab Q3W using a 6+3 design.

- If 0 or 1 of the initial 6 evaluable subjects experience a dose-limiting toxicity (DLT) then the dose combination will be determined to be tolerable and Study Part 2 will be initiated.
- If 2 of the initial 6 evaluable subjects experience a DLT then 3 additional evaluable subjects will be enrolled.
- If 33% or more of the evaluable subjects experience a DLT then the dose combination will be determined to be non-tolerable and a second Part 1 cohort will be enrolled to test a decreased dose of AMG 820 in combination with 200 mg pembrolizumab. Further degree of dose modification and/or schedule of administration will be decided based on analysis of emerging safety and PK data.

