6.2.1.2.5 Cohort Dose Level Determination

Study Part 1

A Dose Level Review Team (DLRT) will convene before a decision is made to open study Part 2. At the start of Part 1, enrollment of the first cohort of 6 to 9 evaluable patients will open for enrollment with a starting dose of AMG 820 1400 mg plus pembrolizumab 200 mg Q3W. Following subject completion of the DLT period, the DLRT will review all available safety data for the first cohort. If the data supports continued dosing at the selected starting dose, study Part 2 will be initiated at the same dose level. If it is determined that the starting dose is non-tolerable (if 33% or more of the evaluable subjects experience a DLT), dose de-escalation will occur and a second Part 1 cohort will be enrolled to test a decreased dose of AMG 820 in combination with 200 mg pembrolizumab Q3W. This will occur until identification of a well-tolerated dose for study Part 2. The AMG 820 (mg) pre-specified nominal cohort dose levels to be explored are 1100 mg and 800 mg Q3W. The pembrolizumab dose level will remain at 200 mg Q3W.

Part 2

Part 2 will have 4 groups, which will be evaluated using a Simon two-stage design:

Table 1. Study Part 2 Subject Groups

Naïve to anti-PD-1/PD-L1/CSF-1/CSF-1R treatment	
Group 1	CRC ^{MMR-proficient}
Group 2	Pancreatic Cancer
Group 3	NSCLC ^{PD-L1 low}
Refractory/ relapsing on anti-PD-1/PD-L1 + naïve to CSF-1/CSF-1R treatment	
Group 4a	NSCLC ^{PD-L1 low}
Group 4b	NSCLC ^{PD-L1 high}

The dose or doses (proposed recommended phase 2 dose, RP2D) to be evaluated in part 2 of the study will be based on results from part 1. The DLRT may determine the RP2D, which is defined as a dose(s) that is/are safe and produces pharmacodynamic effects. Emerging safety data may be used to re-challenge the selected dose in Study Part 1. If the initially selected dose is re-challenged, additional subjects may be enrolled in the corresponding cohort. In addition, the study may be discontinued or modified at any time due to documented safety findings.

Enrollment into the second stage of the Simon two-stage design will be determined by results through Study Part 2 stage 1.

All dose level and enrollment decisions will be formally communicated to investigators via a memorandum.

The dosing schedule is described by a [schema](#) in the protocol synopsis.

6.2.1.3 Dosage Adjustments, Delays, Rules for Withholding or Restarting, Permanent Discontinuation: AMG 820

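### One DLT criterion falls wholly outside the 21-day DLT window and two can still be open when it closes, and no rule says how a pending criterion enters the 6+3 count

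*Protocol*

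**What the plan says.** Protocol Section 6.2.1.2.2 fixes the window: "The DLT evaluation period for a subject is 21 days from the initial administration of study treatment". Section 6.2.1.2.3 ties the DLT list to it: "The occurrence of any of the following toxicities during DLT evaluation period", with investigator-judged relatedness. Three entries on the list depend on elapsed time:

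- "Delay in cycle 2 treatment for > 2 weeks due to study drug-related toxicity", with an exception for steroid tapering clearly due to pembrolizumab alone;
- "Grade 3 non-hematologic toxicity lasting > 7 days despite appropriate treatment";
- a grade 3 or higher non-hematologic laboratory value that persists for more than one week, unless investigator and sponsor both judge it not clinically important.

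On timing, Section 6.2.1.2.2 says that to be evaluable "subjects must have had the opportunity to be on treatment for at least 21 days from the initial dosing" (or have had a DLT in the period). With 0 or 1 DLT in the first 6 evaluable subjects the dose is tolerable and Part 2 starts. With 2, three more subjects are enrolled. With 3 or more it is not tolerable. Section 6.2.1.2.5 says: "Following subject completion of the DLT period, the DLRT will review all available safety data for the first cohort". Section 3.1.1 asks for "at least 21 days of safety follow-up" before a subsequent cohort opens. Section 6.2.1.2.1 lets the combination be declared tolerable on data from the DLT period and states that no DLRM charter will be used.

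SAP Section 6 defines a DLT more briefly, as any related grade 3 or higher adverse event in the 21-day window, and refers to the protocol for detail. SAP Section 10.5.1.1 plans a summary of DLT incidence.

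**The concern.** The window and the list under it do not fit together. A delay counted from day 22 cannot reach two weeks by day 21, and an event that starts on day 17 cannot be shown by day 21 to have lasted more than 7 days. The protocol allows the cohort to be judged once the 21 days are complete. It does not say whether a subject whose cycle 2 is being held, or whose grade 3 event is still running, counts as DLT-free, counts as a DLT, or remains undetermined.

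DLT is a primary endpoint, and its count is the stated numeric rule for opening Part 2. Pending criteria can only lower a count taken at day 21. If they are treated as absent, the decision leans towards tolerable. The subjects enrolled last are the most exposed, because they have the shortest follow-up at the review.

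**Working it through.** **Plan's own figure.** Section 10.2 gives a 47-91% chance of at least one DLT among 6 for true rates of 10-33%. From 1 - (1 - p)^6: 1 - 0.90^6 = 0.469 and 1 - 0.67^6 = 0.910. It reproduces, on the premise that every DLT is known when the count is taken.

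**Calendar check, first dose = day 1.**
- Cycles last 3 weeks (Section 6.2.1.1; Table 5), so cycle 2 is due on day 22. A delay of more than 14 days is first met on day 22 + 15 = 37. With dosing 3 days either side (days 19 to 25), this is day 34 to day 40, that is, 13 to 19 days after the window closes.
- More than 7 days is first reached 7 or 8 days after the onset day, depending on whether the onset day is counted. It can be established by day 21 only for onset by day 13 or 14. Onset on day 21 is settled on day 28 or 29. The one-week laboratory criterion behaves the same way.

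**6+3 rule with nothing pending.** P(tolerable) = P(0 of 6) + P(1 of 6) + P(2 of 6) x (1 - p)^3. At p = 0.33: 0.0905 + 0.2673 + 0.3292 x 0.3008 = 0.457.

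**With a share f of DLTs pending.** The documents give no f. For f = 0.25 the rate counted at the review is q = 0.75 x 0.33 = 0.2475. If 2 of 6 are counted, three more subjects are followed for 21 days. By then the first six are past day 40 and their own pending criteria are settled.

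*All six affected at the first review.*
- 0 or 1 counted: 0.1816 + 0.3583 = 0.5399.
- Exactly 2 counted, the other four truly free of DLT, and none counted in the three added subjects (also affected): 15 x 0.2475^2 x 0.67^4 x 0.7525^3 = 0.0789.
- Total 0.619.

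*Only the last two of six affected.* P(0, 1, 2) is 0.2015, 0.3970, 0.2933 for the first four (rate 0.33) and 0.5663, 0.3725, 0.0613 for the last two (rate 0.2475).
- 0 or 1 counted: 0.2015 x 0.5663 + 0.3970 x 0.5663 + 0.2015 x 0.3725 = 0.4140.
- Exactly 2 counted with no pending DLT behind them: 0.2933 x 0.67^2 + 0.3970 x 2 x 0.2475 x 0.67 + 0.2015 x 0.2475^2 = 0.2757.
- None counted in the added three: 0.67^2 x 0.7525 = 0.3378 if one of them is affected, 0.67 x 0.7525^2 = 0.3794 if two are, 0.7525^3 = 0.4261 if all three are.
- Totals: 0.507, 0.519 and 0.531, so about 51-53%.

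**Range over the assumed share**, same formulas, true rate 33%, all three added subjects affected:

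| Share pending | Last two of six affected | All six affected |
|---|---|---|
| 0 | 46% | 46% |
| 10% | 49% | 52% |
| 25% | 53% | 62% |
| 50% | 60% | 79% |

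**The case against.** The strongest reply has four parts.

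- **The text may be read sensibly.** A toxicity could be taken to arise in the window and be classified later by its duration or by the delay it causes. That is workable, but the section does not say it. Even so, classification could come after the decision the protocol permits.
- **The DLRT is not blind.** A held cycle 2 or an open grade 3 event is visible at the review. Section 10.3.2 requires review of all available data, including data after the window and all grade 3 or higher toxicities short of a DLT, with unanimous decisions. Section 6.2.1.2.3 requires attention to the cumulative adverse event profile. Section 6.2.1.2.1 allows more subjects, a delay in dosing, or reconsideration for late-onset events, and adds three reviews in Part 2 stage 1. Section 6.2.1.2.5 allows the selected dose to be re-challenged. These safeguards are real. But acting on a pending event is discretionary, several come after Part 2 opens, and none sets a waiting or counting rule.
- **Post-window toxicity is covered.** Sections 6.2.1.2.3 and 6.2.1.3 address toxicity meeting the DLT definition after day 21, but for that subject's treatment, not for the cohort count.
- **Little remains to decide.** Amendment 2 records the decision to discontinue investigating the combination, and the SAP covers the final analysis. This stands and limits the practical value of a new waiting rule.

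A reader might also infer more than the documents support. No section fixes the review on day 22, since 21 days is a minimum. No section directs that a pending subject be scored as DLT-free; the documents are silent. Reported DLT incidence need not be biased, because durations and delays will be known by the final analysis; bias would follow only from the strictest literal reading. Applying a counted rate of 25% to every subject at both reviews would give 66%, but this ignores that the first six subjects' pending events settle before the 9-subject review.

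**Conclusion.** The point holds as an internal contradiction. The cycle 2 delay criterion cannot be met inside the stated window. The 7-day grade 3 and one-week laboratory criteria are affected only for onset in about the last week. Because the protocol neither waits for pending criteria nor says how to count them, the last-enrolled subjects can be taken as DLT-free while a criterion is open.

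The calendar finding rests on the protocol alone. The effect on the decision does not: the pending share and the number of subjects affected are assumptions. At a true rate of 33%, a quarter pending moves the chance of declaring the dose tolerable from 46% to about 51-53% (last two of six) or about 62% (all six, as if enrolled nearly together). These figures give no credit for DLRT discretion, which could bring them down. The direction is clear; the size is not.

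**What to change.** Reconcile three things in Protocol Sections 3.1.1, 6.2.1.2.2, 6.2.1.2.3 and 6.2.1.2.5: the 21-day window, the delay and duration criteria, and the timing of the cohort decision. The choice of window and criteria is the sponsor's. The text should then state:

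- whether a toxicity that begins in the window but reaches its duration or delay threshold afterwards counts as a DLT;
- that a subject's DLT status is not final for the 6+3 count while any listed criterion is pending.

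Apply the same counting rule to the DLT summary in SAP Section 10.5.1.1, and bring the short definition in SAP Section 6 into line with the protocol. As it stands, the short definition ignores duration and omits the delay criterion.

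The cost is wording, plus a DLRM that may wait up to about 2-3 weeks (day 37 to 40 against day 21), and only when a cycle 2 dose is held or an event is open. With the combination being discontinued, the waiting rule may affect no further decision; the counting rule still governs how DLT incidence is reported.
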